**Table 6: Hypertension management plan**

## 5.12 Axitinib/Placebo Dose Reduction for Proteinuria

- If dipstick shows > 2+ proteinuria, perform 24 hour urine collection. Dosing may continue while waiting for test results.
- If < 3.5 g proteinuria/24 hour is reported, continue dosing at the same dose level.
- If > 3.5 g proteinuria/24 hours is reported, hold dosing and repeat 24 hour urine collection for proteinuria and creatinine clearance (interval at investigator discretion) until proteinuria is < 3.5 g/24 hours. Restart Axitinib/placebo at the same dose or one lower dose level at the discretion of the investigator.

Patients removed from treatment for intolerable toxicity should still be followed with regular tumour assessments until disease progression or start of new treatment, and for survival thereafter.

### **5.13 Axitinib/Placebo Dose Interruption for Surgery or Surgical Procedures**

If a major surgery or an interventional procedure (eg, endoscopy) is required, treatment with Axitinib/placebo must be interrupted at least 24 hours before the procedure and the patient blood pressure should be monitored closely for hypotension. Patients may receive further study treatment 2 weeks after surgery or 1 week after interventional procedure based on the judgment of the treating physician and principal investigator, if the reason for procedure is other than disease progression.

### **5.14 Compliance**

Patients will maintain diaries to include missed or changed doses. Pill counts on returned study drug bottles should be performed.

### **5.15 Drug Storage and Drug Accountability**

Axitinib/placebo will be supplied for the study by the Pharmacy Operations Office, Pfizer. CTM will be shipped to the study sites with an Investigational Drug Receipt Confirmation form. This form should be completed with protocol number, drug name, lot number, quantity received and condition upon receipt. A copy of the form must be returned via fax to the Pharmacy Operations Office within 24 hours of receipt. A copy will also be returned via mail. The investigator, or an approved representative (eg, pharmacist), will ensure that all Axitinib/placebo is stored in a secured area, under recommended storage conditions and in accordance with applicable regulatory requirements. Drug should be stored at controlled room temperature (ie, 15-30°C), and protected from light and moisture. To ensure adequate records, all Axitinib/placebo will be accounted for in the case report form and drug accountability inventory forms as instructed by Pfizer. Unless otherwise authorized by Pfizer, at the end of the clinical trial all drug supplies unallocated or unused by the subjects must be returned to Pfizer.

Axitinib/placebo is considered a hazardous drug (due to possible reproductive toxicity), and should be handled according to the recommended procedures described in the current edition of the ASHP, Technical Assistance Bulletin on Handling Cytotoxic and Hazardous Drugs, AHFS Drug Information (1999) and its references. Procedures described in each

institution's pharmacy or hospital standard operating procedure manual should be followed when handling hazardous drugs.

## **5.16 Concomitant Medication(s)**

No other chemotherapy or experimental anticancer medications will be permitted while the patient is on study. Any disease progression requiring other forms of systemic anticancer therapy will be cause for discontinuation from study treatment. Palliative radiotherapy is allowed for pain control ONLY to sites of bone disease present at baseline.

## **5.17 Axitinib/Placebo**

Palliative and supportive care for disease-related symptoms, including pain medications, will be allowed to all patients on this trial. Patients may receive loperamide or other medications for treatment or prophylaxis of potential diarrhoea. Anti-inflammatory or narcotic analgesics may be offered as needed. Patients with fever or infection may undergo diagnostic tests and treated with antibiotics as appropriate and may receive therapeutic colony-stimulating factors as appropriate. Erythropoietic agents such as epoetin or darbepoetin may be used at the discretion of the treating physician. Packed red blood cell and platelet transfusions should be administered as clinically indicated. Low-dose oral steroids (defined as <5 mg per day prednisone or equivalent), short course of oral steroids (defined as <5 consecutive days) or topical or inhaled steroids at any dose may be taken during the study.

Patients who need to be on anticoagulant therapy during treatment with Axitinib/placebo should be treated with low molecular weight heparin as the preferred therapy. The administration of coumadin or other coumarin derivatives may be allowed; however, due to possibility of inhibition of CYP1A2-mediated metabolism of coumadin by Axitinib, appropriate monitoring of PT/INR should be performed for any potential increased Coumadin concentration.

In vitro studies with human liver microenzymes and recombinant CYP enzymes indicated that Axitinib metabolism was primarily mediated by the drug-metabolizing enzyme CYP3A4/5, and to a lesser extent by CYP1A2, CYP2C19 and uridine glucuronosyltransferase (UGT) 1A1. Clinically, there is likelihood that Axitinib plasma concentrations may be increased in the presence of co-administered potent inhibitors of the CYP3A4/5 enzymes. In a healthy volunteer study, ketoconazole, a potent CYP3A4/5 inhibitor, produced a 2-fold increase in plasma exposure and a 1.5-fold increase in peak plasma concentration of Axitinib. Therefore a potential exists for drug-drug interactions with potent CYP3A/5 inhibitors such as grapefruit juice, ketoconazole, nefazodone, itraconazole, miconazole, erythromycin, clarithromycin, telithromycin, verapamil, indinavir, saquinavir, ritonavir, nelfinavir, lopinavir, atazanavir, amprenavir, fosamprenavir and delavirdine. Patients who require concomitant treatment with CYP3A/5 inhibitors are not eligible for this study.

Axitinib metabolism may be induced in patients taking potent CYP3A4/5 or CYP1A2 inducers (carbamazepine, dexamethasone, felbamate, omeprazole, phenobarbital, amobarbital, phenytoin, primidone, rifabutin, rifampin, nevirapine, and St John's wort) and this may reduce Axitinib plasma concentrations. Patients who require concomitant treatment with potent CYP3A4/5 or CYP1A2 inducers are not eligible for the study. Since CYP1A2 is also known to be induced in chronic smokers, there is likelihood that Axitinib plasma concentrations may be reduced in these individuals. (Note: these patients are not excluded from enrolment, however.)

The ability of Axitinib to increase concentrations of co-administered drugs was also investigated in studies with human liver microsomes. At expected therapeutic plasma concentrations (0.01 to 1.0 µg/mL), Axitinib appears most likely to inhibit the drug metabolizing enzymes CYP1A2 and CYP2C8, 2 enzymes not frequently observed as predominant drug metabolizing enzymes. Theophylline and tacrine are among the few drugs whose plasma concentrations are likely to be increased by Axitinib.

Axitinib is highly bound to proteins in human plasma (99.0% bound at concentrations between 0.2-20 µg/mL). Therefore, drug interactions with other agents that are also highly bound to plasma proteins are a possibility.

Patients who need to be on chronic antacid therapy with histamine H2 antagonists (e.g., cimetidine [Tagamet®], famotidine [Pepcid®], nizatidine [Axid®], ranitidine [Zantac®]), proton-pump inhibitors (eg, lansoprazole [Prevacid®], rabeprazole [Aciphex®], pantoprazole [Protonix®], and esomeprazole [Nexium®]), or locally acting antacids (eg, Maalox®, Milk of Magnesia®, Amphojel®) should stagger the timing of their Axitinib and antacid dosing. Patients should avoid use of antacids for 2 hours before through 2 hours after taking Axitinib/placebo tablets. Note, however, that patients taking the proton-pump inhibitor omeprazole (Prilosec®) are not eligible for this study and that patients should not use omeprazole while taking Axitinib/placebo tablets because omeprazole is a CYP1A2 inducer.

Axitinib is not likely to have drug-drug interactions with commonly used antihypertensive agents belonging to the class of ACE inhibitors including angiotensin II receptor antagonists (e.g., enalapril, captopril, losartan, valsartan), beta-blockers (e.g., atenolol, metoprolol, labetalol), or diuretics (e.g., hydrochlorothiazide, furosemide). Within the class of calcium channel blockers, verapamil, and to a lesser extent nifedipine, nicardipine, and diltiazem have a potential for increasing plasma Axitinib plasma concentrations, due to CYP3A4/5 inhibition and should not be used as first choice in antihypertensive treatment. Other calcium channel blockers (e.g., amlodipine, bepridil, felodipine) are less likely to raise Axitinib plasma levels.

The above information is based on preclinical data from studies using human and animal metabolising enzyme systems.

All concomitant medications and blood products, as well as interventions (e.g., analgesic use or paracentesis) received by patients from the first dose of Axitinib until the end of study visit will be recorded on the CRF.

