15. Known human immunodeficiency virus (HIV) infection.
16. Pregnancy, breastfeeding, or unwillingness/inability to employ an effective method of birth control/contraception to prevent pregnancy during treatment and for up to 3 months after discontinuing study drug if of reproductive potential.
17. Other severe acute or chronic medical or psychiatric condition, or laboratory abnormality that would impart, in the judgement of the investigator, excess risk associated with study participation or study drug administration, or which, in the judgment of the investigator would make the patient inappropriate for entry into the trial.
18. Gastrointestinal abnormalities including: inability to take oral medication; requirement for intravenous alimentation; prior surgical procedures affecting absorption; treatment for active peptic ulcer disease in the past 6 months; active gastrointestinal bleeding, unrelated to cancer, as evidenced by hematemesis or melaena in the past 3 months without evidence of resolution documented by endoscopy or colonoscopy;
19. Current use or anticipated need for treatment with drugs that are known CYP3A4 or CYP1A2 inducers (i.e. carbamazepine, dexamethasone, felbamate, omeprazole, phenobarbital, phenytoin, amobarbital, nevirapine, primidone, rifabutin, rifampin, and St. John's wort).

20. Current use or anticipated need for treatment with drugs that are known CYP3A4 inhibitors (i.e. grapefruit juice, ketoconazole, nefazodone, itraconazole, miconazole, erythromycin, clarithromycin, telithromycin, verapamil, indinavir, saquinavir, ritonavir, nelfinavir, lopinavir, atazanavir, amprenavir, fosamprenavir and delavirdine)
21. Any of the following within 6 months prior to study drug administration: myocardial infarction, uncontrolled angina, coronary/peripheral artery bypass graft, symptomatic congestive heart failure, cerebrovascular accident or transient ischemic attack and 6 months for deep vein thrombosis or pulmonary embolism.

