## 5.8 Dosing

The recommended starting dose of Axitinib is 5 mg bd taken orally with food. Dose adjustments, including dose increase or dose reduction should be based on adverse events experienced by the individual patient. Axitinib should be taken beginning on Day 1 of the study. Doses should be taken approximately 12 hours apart continuous dosing.

Patients will be instructed to take their doses at approximately the same times each day. Patients will be instructed that if they vomit after taking a dose, that they must not take an extra dose, but instead resume subsequent doses as prescribed. Any missed dose may be taken late up to 3 hours before the next scheduled dose, otherwise, it should be skipped. If doses are missed or vomited, this must be indicated in the source documents and CRFs. Study treatment will be administered in cycles of 4 weeks in duration.

Patients who tolerate Axitinib with no adverse events related to study drug above CTCAE Grade 2 for consecutive 2-week period should have their dose increased by one dose level (see Table 4) to a maximum of 10 mg bd (unless the patient's blood pressure is >150/90 mm Hg or the patient is receiving antihypertensive medication). Patients experiencing drug reaction greater than CTCAE Grade 2 should undergo dose modification. For the patients receiving Axitinib, concomitant medications that are known to substantially inhibit the enzyme, CYP3A4, should be avoided as much as medically possible. The clinical judgment, taking into account all of these parameters, of the treating physician should be exercised in titrating Axitinib dose.

Available Axitinib Dose Levels	Dose
+2	10 mg BD
+1	7 mg BD
0 (Starting Dose)	5 mg BD
-1	3 mg BD
-2	2 mg BD

Table 4: Axitinib dose modification table

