## 5.11 Axitinib/Placebo Dose Reduction for Hypertension

Patients treated with Axitinib/placebo will be issued blood pressure cuffs (provided by Pfizer Inc) for home monitoring and instructed to measure their blood pressure (BP) twice daily, prior to taking each dose. All blood pressure measurements will be recorded in a diary and brought to the nurse or study coordinator at each clinic visit. Patients should be instructed by the study staff to contact their physician for guidance if their systolic blood pressure rises above 140 mm Hg, diastolic blood pressure rises above 90 mm Hg, or if they develop symptoms perceived to be related to elevated BP (eg, headache, visual disturbance). See below for dose modifications for hypertension. A different blood pressure threshold for contacting physician may be used according to the physician's clinical judgment. See below for dose modifications for hypertension.

New or additional antihypertensive therapy (see Section 5.4, Concomitant Medication(s) for guidance) should be started if 2 BP readings, preferably taken in the clinic and separated by at least 1 hour, show the following: 2 systolic BP readings greater than 140 or 2 dBP readings greater than 90 mm Hg. Alternately, the dose of existing antihypertensive medication(s) may be increased. Investigator may use clinical judgment to start new or additional antihypertensive therapy at a lower blood pressure threshold. If the patient is already on maximal antihypertensive treatment, the Axitinib dose should be reduced by 1 dose level (see Table 4).

Patients who have 2 systolic BP readings, separated by at least 1 hour, greater than 160 mm Hg, or 2 dBP readings, separated by at least 1 hour, greater than 105 mm Hg, will have treatment with Axitinib/placebo held. (Note: if Axitinib/placebo is held, patients receiving antihypertensive medications should monitor closely for hypotension and restart Axitinib/placebo at one lower dose level (see Table 4) as soon as BP is <140/90 mm Hg. The plasma half-life of Axitinib is 2 – 4 hours and BP usually decreases within 1-2 days following dose interruption.)

Patients removed from treatment for intolerable toxicity should still be followed with regular tumour assessments until disease progression or start of new treatment, and for survival thereafter.

Degree of Blood Pressure Elevation			
Systolic Pressure	OR	Diastolic Pressure	Management

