2 BP readings separated by at least 1 hour show systolic pressure >150 mm Hg		2 BP readings separated by at least 1 hour show diastolic pressure >100 mm Hg	If not on maximal antihypertensive treatment, institute new or additional antihypertensive medication and maintain dose of Axitinib.  If on maximal antihypertensive treatment, reduce Axitinib to one lower dose level.
2 BP readings separated by at least 1 hour show systolic pressure >160 mm Hg	OR	2 BP readings separated by at least 1 hour show diastolic pressure >105 mm Hg	Stop Axitinib; adjust antihypertensive medication; as soon as BP is less than 150/100 mm Hg, restart Axitinib at one lower dose level.
Recurrent hypertension following previous dose reduction (2 BP readings separated by at least 1 hour show systolic pressure >150 mm Hg)	OR	Recurrent dBP >100 mm Hg (2 BP readings separated by at least 1 hour) following previous dose reduction	Repeat Axitinib dose reduction by one lower dose level. If a patient requires dose reduction below 2 mg BD, contact Sponsor for discussion

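### Verapamil, a listed CYP3A4/5 inhibitor that makes a patient ineligible at entry, is not barred on study as a later-line antihypertensive, and 5.11 points to the wrong section for guidance

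*Combined protocol and SAP*

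**What the plan says.** **At entry.** Section 4.2, exclusion 20, rules out "Current use or anticipated need for treatment with drugs that are known CYP3A4 inhibitors" and names verapamil in its list. Section 5.17 repeats that list, warns that a "potential exists for drug-drug interactions with potent CYP3A/5 inhibitors such as grapefruit juice" and the other named drugs, verapamil among them, and concludes: "Patients who require concomitant treatment with CYP3A/5 inhibitors are not eligible for this study".

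**On study.** Section 5.8 says that "concomitant medications that are known to substantially inhibit the enzyme, CYP3A4, should be avoided as much as medically possible". Later in 5.17, the paragraph on antihypertensives says that verapamil, and to a lesser extent nifedipine, nicardipine and diltiazem, may raise axitinib concentrations "due to CYP3A4/5 inhibition and should not be used as first choice in antihypertensive treatment". The same paragraph names drugs with less or no expected interaction: ACE inhibitors and angiotensin II antagonists, beta-blockers, diuretics, and other calcium channel blockers such as amlodipine and felodipine.

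**Managing hypertension.** In the first tier of Table 6, for a patient not on maximal antihypertensive treatment, the instruction is to "institute new or additional antihypertensive medication and maintain dose of Axitinib". The text of 5.11 reads: "New or additional antihypertensive therapy (see Section 5.4, Concomitant Medication(s) for guidance) should be started if 2 BP readings".

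**The concern.** Hypertension is a common effect of axitinib, and the protocol responds to it first with antihypertensive drugs. One of the drugs left open for that purpose is on the protocol's own list of inhibitors of axitinib metabolism. Adding it at an unchanged axitinib dose could raise exposure in a patient who is already hypertensive on the drug. A prescriber who looks for guidance at that moment is sent to a section about drug supply. What is at stake is patient safety in a small number of cases, not the validity of the efficacy analysis.

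**Working it through.** The plan states no figure on this point, so the check is a comparison of texts, followed by one piece of arithmetic for context.

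1. **Entry rule against on-study rule.** Exclusion 20 and the sentence in 5.17 are worded as eligibility rules. Axitinib-related hypertension arises after entry, so they do not settle what may be prescribed then. The only on-study sentence that names verapamil (5.17) removes it as first choice. Second or later choice remains open, subject to the general advice in 5.8, which is not a ban.

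2. **Comparison with omeprazole.** Omeprazole is also on an exclusion list (exclusion 19). For it, 5.17 states ineligibility and then adds an on-treatment rule: "patients should not use omeprazole while taking Axitinib/placebo tablets because omeprazole is a CYP1A2 inducer". Verapamil has no matching sentence. Nor has any other inhibitor in exclusion 20: ketoconazole, erythromycin and clarithromycin, for example, are covered on study only by 5.8, while 5.17 allows antibiotics as appropriate. The gap is therefore wider than verapamil, although verapamil is the one named for treating axitinib's own toxicity.

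3. **What happens to the axitinib dose.** Table 6 has three tiers:
   - Above 150/100 mm Hg and not on maximal treatment: add a drug and keep the dose. If already on maximal treatment: reduce one level.
   - Above 160/105: stop, then restart one level lower.
   - Recurrence after an earlier reduction: reduce again.

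   The dose is thus maintained only in the first tier below maximal treatment. No section requires a reduction because an inhibitor has been added.

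4. **Cross-reference.** Section 5.11 cites 5.4 under the title Concomitant Medication(s). Section 5.4 is Drug Supplies. Section 5.16 carries that title but deals with anticancer therapy and palliative radiotherapy. The antihypertensive guidance is in 5.17.

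5. **How often the choice of antihypertensive may arise.** Table 1 gives hypertension in the solid-tumour single-agent column as 56/128 = 43.75%, and at Grade 3/4 as 22/128 = 17.2%. With 50 patients at 2:1, the axitinib arm has 50 × 2/3, or about 33. At the Table 1 rates, 0.4375 × 33 = 14.4 and 0.172 × 33 = 5.7, so about 14 and 6 patients. These are patients with hypertension, for whom a drug may have to be chosen. They are not an estimate of verapamil users, for which the documents give no rate.

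**The case against.** The strongest reply is that the protocol already deals with most of this. Because 5.17 itself places verapamil among the potent inhibitors, the advice in 5.8 applies to it, and with several alternative classes named, avoidance should nearly always be possible. A patient on maximal treatment has axitinib reduced. Patients measure blood pressure at home twice daily and call above 140/90, it is checked at every clinic visit, and Table 5 reduces or interrupts dosing for most Grade 3-4 related toxicity. Entry criteria that are stricter than on-study rules can also be deliberate.

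Most of that stands. It reduces the gap to a late-line case and makes this a permissive rule rather than a contradiction. It does not close the gap: ruling a drug out as first choice implies that it may be used later, and the omeprazole sentence shows that the protocol states an on-treatment ban where it intends one. One control is also uneven. Section 5.8 withholds dose increases from patients on antihypertensives, while the Trial Treatment text in the Trial Summary and in Section 3 gives only the blood pressure limit.

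A reader might infer that Table 6 steers prescribers towards later-choice drugs such as verapamil. It does not; it asks for a new or additional antihypertensive, and for an untreated patient that is a first-choice drug, where verapamil is advised against.

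**Conclusion.** The point holds as a minor safety matter that is cheap to correct. A drug that makes a patient ineligible at entry is left available on study as a later-line antihypertensive at a maintained axitinib dose, and the pointer to the relevant guidance is wrong. The number of patients affected cannot be estimated but should be small, given the alternatives in 5.17. This rests on reading the ineligibility sentence in 5.17 as an entry rule, which is how it is worded.

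Three stronger readings are not supported:

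- **A quantified overdose, or a mandatory dose reduction.** The documents give no exposure figure for verapamil; 5.17 describes this information as preclinical. The 2-fold rise in exposure quoted there is for ketoconazole in healthy volunteers and cannot be carried over. A fixed reduction for an interaction of unknown size could under-dose the patient or fail to compensate.
- **Bias in the pharmacokinetic correlations.** Samples taken after an inhibitor is started would reflect it, but no effect on the planned correlations has been shown.
- **Damage to the efficacy analysis.** Nothing here changes the sample size, any stated figure or the primary endpoint.

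**What to change.** 1. In the antihypertensive paragraph of 5.17, replace the first-choice restriction on verapamil with a statement that it should not be used during axitinib/placebo treatment, on the model of the omeprazole sentence, and direct prescribers to the alternatives already named there. Nifedipine, nicardipine and diltiazem, which are not in exclusion 20, can keep the present restriction.
2. State in 5.8 and 5.17 that the on-study avoidance rule covers all inhibitors listed in exclusion 20. If one is unavoidable, the site contacts the sponsor; no automatic dose reduction applies.
3. Correct the reference in 5.11 from 5.4 to 5.16/5.17.
4. Optionally, use the concomitant-medication CRF entries to flag pharmacokinetic samples taken on a listed inhibitor.

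The cost is a few sentences and one section number. Clinicians lose one late-line antihypertensive. The rule applies to axitinib and placebo alike, so blinding is unaffected, and the optional flag needs no new data.
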